6.2 DATA SHARING PLANS

6.2.1 Human Data Sharing Plan

I will share coded, linked human data generated in this research for future research

- in a NIH-funded or approved public repository clinicaltrials.gov, dbGaP
- in BTRIS
- with approved outside collaborators under appropriate agreements
- in publication and/or public presentations

at the time of publication or shortly thereafter.

6.2.2 Genomic Data Sharing Plan

Unlinked genomic data will be deposited in public genomic databases such as dbGaP in compliance with the NIH Genomic Data Sharing Policy.

6.3 RESPONSE CRITERIA

For the purposes of this study, patients should be re-evaluated for response every 9 weeks. In addition to a baseline scan, confirmatory scans should also be obtained 4-8 weeks following initial documentation of objective response.

Response and progression will be evaluated in this study using the new international criteria proposed by the revised Response Evaluation Criteria in Solid Tumors (RECIST) guideline (version 1.1)[82] and Modified Immune-related response criteria (irRC) [Appendix B](#). Changes in the largest diameter (unidimensional measurement) of the tumor lesions and the shortest diameter in the case of malignant lymph nodes are used in the RECIST criteria.

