3.5 STUDY CALENDAR

	Screening	Baseline	Cycles 1-6⁵	Cycle 7- to PD⁵	EOT⁹	Follow Up¹⁰
Pembrolizumab ¹			X	X		
Oxaliplatin ²			X			
Capecitabine ³			X			
Informed consent	X					
Medical history ⁴	X	X				
Concomitant meds			X	X		
Adverse event evaluation			X	X	X	
Physical exam ⁴	X	X	X	X	X	
Vital signs ⁴	X	X	X	X	X	
Height	X					
Weight ⁴	X		X	X		
Performance Status ⁴	X		X	X	X	
CBC w/differential, Platelets ⁴	X		X ¹³	X ¹³	X	
PT, INR, PTT, Fibrinogen			X ¹³	X ¹³	X	
Serum chemistry ^{4, 12}	X		X ¹³	X ¹³	X	
HIV, Hepatitis B and C serology and/or viral load	X					
HLA		X				
Thyroid Panel			X ¹³	X ¹³	X	
TB testing (if clinically indicated)	X					
Serum or urine pregnancy test ⁴	X	X				

	Screening	Baseline	Cycles 1-6 ⁵	Cycle 7- to PD ⁵	EOT ⁹	Follow Up ¹⁰
Tumor markers: aFP, CEA or Ca 19.9 ⁴			X ¹³	X ¹³		
EKG ⁴	X	X				
Confirmation of dx by NCI LP	X					
Restaging radiologic Evaluation ⁴	X	X	X ⁶	X ⁶		
Optional Tumor biopsy		X	X ⁷			
Immune monitoring ¹¹			X	X		
Blood for TCR beta sequencing ¹⁴			X	X		
Advance Directive ⁸		X				
Annual telephone contact						X

¹ 200 mg of Pembrolizumab will be administered as a 30-minute IV infusion Day 1 of each cycle.

² Oxaliplatin will be administered on D1 of each cycle at a dose of 130mg/m² IV

³ Capecitabine will be administered at a dose of 750 mg/m² PO every 12 hours. Doses will be rounded downward to the nearest 150 mg. Patients will begin Capecitabine dosing on the Day 1 of each cycle and will continue to receive Capecitabine for 14 days.

⁴ Tests performed at screening do not need to be repeated on baseline or Cycle 1 Day 1 if performed in designated time frame

⁵ Each cycle is 21 days. Trial treatment may be administered up to 3 days before or after the scheduled Day 1 of each cycle due to administrative reasons.

⁶ CT/PET/MRI of chest abdomen and pelvis. Restaging scans every 9 weeks +/- 7 days.

⁷ Performed on cycle 3 Day 1 only +/- 7 days

⁸ As indicated in section **10.3**, all subjects will be offered the opportunity to complete an NIH Advance Directive form. This should be done preferably at baseline but can be done at any time during the study as long as the capacity to do so is retained. The completion of the form is strongly recommended but is not required.

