3.6.1 Criteria for Removal from Protocol Therapy

Treatment may continue until one of the following criteria applies:

- Disease progression (per immune-related response criteria).
- Intercurrent illness that prevents further administration of treatment
- Unacceptable toxicity as defined in section **3.4**
- Participant requests to be withdrawn from active therapy
- General or specific changes in the patient's condition render the patient unacceptable for further treatment in the judgment of the investigator
- Delayed recovery from toxicity that prevents re-treatment in ≤ 28 days of scheduled therapy
- Investigator discretion
- Positive pregnancy test

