8 STATISTICAL CONSIDERATIONS

The primary objective of this study is to determine in a preliminary, limited size trial whether Pembrolizumab in combination with CAPOX is associated with a 5-month progression free probability, which exceeds 25% when used to treat patients with biliary tract cancer.

Based on our analysis of data from previous trials of patients with similar eligibility requirements the median progression free survival in biliary tract carcinoma is 2.5 months. This translates to 25% without progressive disease at 5 months following an exponential failure model. Based on these results, it would be useful to demonstrate whether Pembrolizumab in combination with CAPOX is able to be associated with a median PFS of 5 months, which would correspond to 50% of patients having stable disease at 5 months. The trial will be conducted using a two-stage optimal design (Simon R, Controlled Clinical Trials, 10:1-10, 1989). In order to attempt to determine if the agent offers any improvement, using alpha=0.10 and beta =0.10 as acceptable error probabilities, the trial will target 50% as the desirable proportion of patients who are still without progression at the five-month evaluation ($p_1=0.50$), and will be considered inadequate if only a fraction consistent with 20% are without progression by the same evaluation time ($p_0=0.20$).

Initially, 10 patients will be enrolled and evaluated for progression. Enrollment will be temporarily halted after the 10th patient has been accrued, unless we know that 3 patients have passed the 5-month point without progression. If 3 or more of the first 10 patients enrolled have not progressed at the 5-month evaluation, then accrual will continue until a total of 17 patients have been entered. If, among the first 10 patients accrued, 0 to 2 are able to be progression-free at the 5-month evaluation, then no further patients will be enrolled after such a determination has been made. If 6 or more of the total cohort of 17 patients have been found to be progression-free at 5 months, then this will indicate an adequate progression free probability to justify further consideration of Pembrolizumab in combination with CAPOX in this population of patients. On the other hand, if 3 to 5 of 17 are progression-free at 5 months, this will be considered

insufficient. Under the null hypothesis (20% progression free at 5 months), the probability of being able to stop accrual after 10 patients have been evaluated at 5 months is 68%.

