In addition to evaluation of the proportion of patients that are progression-free at 5 months, the progression-free survival for patients will also be analyzed via a Kaplan-Meier curve. This curve will be compared informally to other published results in similar patients. As well, the overall response rate will be reported, and the overall survival will be reported using a Kaplan-Meier curve. It is anticipated that up to 10 patients per year will be able to enroll onto this protocol. Thus, it is expected that accrual of up to 17 total patients can be completed in approximately 2 years. In order to allow for a small number of unevaluable patients, the accrual ceiling will be set at 19 patients.

To evaluate the response rate, proportion of patients obtaining CR and PR per RECIST 1.1 criteria of all evaluable patients will be analyzed.

To address safety, tolerability and feasibility of Pembrolizumab in combination with CAPOX chemotherapy, adverse events will be tabulated by grade according to CTCAE and analyzed and reported descriptively.

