13.2 APPENDIX B- MODIFIED IMMUNE-RELATED RESPONSE CRITERIA (irRC)

This new classification is based on the recent learning from clinical studies with cancer immunotherapies that even if some new lesions appear at the beginning of a treatment or if the total tumor burden does not increase substantially, tumor regressions or stabilizations might still occur later. The irRC were created using bi-dimensional measurements (as previously widely used in the World Health Organization criteria). For this trial, the concepts of the irRC are combined with RECIST 1.1 to come up with the modified irRC.

For modified irRC, only target and measurable lesions are taken into account. In contrast to the RECIST 1.1 criteria, the modified irRC criteria (a) require confirmation of both progression and response by imaging at 6 weeks after initial imaging and (b) do not necessarily score the appearance of new lesions as progressive disease if the sum of lesion diameters of target lesions (minimum of 10 mm per lesion, maximum of 5 target lesions, maximum of 2 per organ) and measurable new lesions does not increase by $\geq 20\%$.

The same method of assessment and the same technique should be used to characterize each identified and reported target lesion(s) at baseline, during the trial, and at the end of trial visit. All measurements should be recorded in metric notation. The modified irRC based on RECIST 1.1 are displayed below.

Modified immune-related response criteria are defined as follows:

New measurable lesions: Incorporated into tumor burden.

New non-measurable lesions: Do not define progression but precludes (irCR).

Overall irCR: Complete disappearance of all lesions (whether measurable or not) and no new lesions. All measurable lymph nodes also must have a reduction in short axis to 10 mm.

Overall irPR: Sum of the longest diameters of target and new measurable lesions decreases $\geq 30\%$.

Overall irSD: Sum of the longest diameters of target and new measurable lesions neither irCR, irPR, (compared to baseline) or irPD (compared to nadir).

Overall irPD: Sum of the longest diameters of target and new measurable lesions increases $\geq 20\%$ (compared to nadir), confirmed by a repeat, consecutive observations at least 4 weeks (normally it should be done at 6 weeks) from the date first documented.

Overall Responses Derived from Changes in Index, Non-Index, and New Lesions

Measurable Response	Non-Measurable Response		Overall Response Using Modified irRC

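### Section 8 does not say whether RECIST 1.1 or modified irRC progression decides the primary 5-month count, and one patient scored differently can reverse the go/no-go decision

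*Combined protocol and SAP*

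**What the plan says.** Section 6.3 names two criteria for both response and progression and gives no order between them: "Response and progression will be evaluated in this study using the new international criteria" of RECIST 1.1 "and Modified Immune-related response criteria (irRC". Section 6.4 adds that irRC are *also* employed, without calling them supportive.

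Section 8 defines the primary count only as patients without progression at 5 months. The first-stage rule reads "If 3 or more of the first 10 patients enrolled have not progressed at the 5-month evaluation", and the final rule needs 6 of 17. No criterion is attached to either. RECIST 1.1 is named in Section 8 only for the secondary response rate: "proportion of patients obtaining CR and PR per RECIST 1.1 criteria of all evaluable patients will be analyzed".

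Section 3.6.1 ends protocol therapy on "Disease progression (per immune-related response criteria".

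Appendix B says that modified irRC "do not necessarily score the appearance of new lesions as progressive disease" and that irPD must be "confirmed by a repeat, consecutive observations at least 4 weeks" later, normally 6 weeks. Elsewhere the same appendix puts confirmation at 6 weeks. The study calendar (Section 3.5) has "Restaging scans every 9 weeks +/- 7 days".

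**The concern.** The primary endpoint is a count in at most 17 patients with sharp cut-offs, and the event being counted has two definitions in the same protocol. Two analysts following the text could score the same scans differently and reach opposite conclusions about whether the combination merits further study.

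The trial is open-label (Section 11.1.3) with one arm (Section 2.3.1), and the principal investigator reviews each patient's response data (Section 7.4). A choice of criterion left until the scans are known is therefore exposed to bias, even if unintended. The stated 10% error rate also has meaning only if the null rate and the trial count refer to the same kind of progression.

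**Working it through.** **1. How the definitions differ**

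| Finding | RECIST 1.1 (Sections 6.3.4.1 to 6.3.4.3) | Modified irRC (Appendix B) |
|---|---|---|
| New lesion | Progression | Measurable: added to the sum. Non-measurable: does not define progression |
| Unequivocal non-target progression, sum up by less than 20% | Progression | irSD |
| Sum up by 20% or more from the smallest value | Progression if also at least 5 mm | irPD; no absolute minimum stated |
| Confirmation of progression | Not asked for in the target-lesion definition | Required |

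The first, second and fourth rows make irRC the more lenient. The third can go the other way, because only RECIST has the 5 mm condition. So irRC would usually, not always, give an equal or higher progression-free count.

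**2. The plan's design reproduced**

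Inputs from Section 8: p0 = 0.20, p1 = 0.50, alpha = beta = 0.10; continue if at least 3 of 10, go if at least 6 of 17.

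- P(stop early) = Σ over x = 0 to 2 of C(10,x) pˣ(1−p)¹⁰⁻ˣ. At p = 0.20 this is 0.107 + 0.268 + 0.302 = 0.678 (stated: 68%).
- P(go) = Σ over x = 3 to 10 of C(10,x) pˣ(1−p)¹⁰⁻ˣ × P(Bin(7,p) ≥ max(0, 6−x)). This gives 0.094 at p = 0.20 and 0.904 at p = 0.50.

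A search over two-stage designs with up to 35 patients returns this same design as optimal. The design arithmetic is sound.

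**3. Effect of counting under irRC**

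Let p be the progression-free rate under RECIST and d the share of RECIST progressors still progression-free under irRC at 5 months. The protocol gives no value for d; 5%, 10% and 20% are assumptions. Taking every irRC progression to be a RECIST progression as well, the apparent rate is q = p + (1 − p)d. At p = 0.20:

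- d = 5%: q = 0.20 + 0.80 × 0.05 = 0.24
- d = 10%: q = 0.20 + 0.80 × 0.10 = 0.28
- d = 20%: q = 0.20 + 0.80 × 0.20 = 0.36

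Putting q into the P(go) formula:

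| RECIST rate p | P(go), RECIST count | irRC count, d = 5% | d = 10% | d = 20% |
|---|---|---|---|---|
| 0.20 | 0.094 | 0.185 | 0.304 | 0.574 |
| 0.35 | 0.541 | 0.646 | 0.738 | 0.875 |
| 0.50 | 0.904 | 0.933 | 0.955 | 0.981 |

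Under the same assumption, the difference from the RECIST column is the probability that the two criteria give opposite final decisions: about 0.09, 0.21 and 0.48 at p = 0.20, and 0.03, 0.05 and 0.08 at p = 0.50.

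**4. Timing of confirmation**

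Five months is 5 × 30.4375 / 7 = 21.7 weeks. Scheduled scans fall at nominal weeks 9, 18 and 27. Progression first seen at week 18 would be confirmed at week 18 + 4 = 22 to 18 + 6 = 24, nominally just after the 5-month point. The ±7-day window allows week 17 + 4 = 21, which is before it. The protocol does not say whether irPD is dated at the first or the confirming scan. The extra scan 4 to 8 weeks later in Section 6.3 is for objective response, not progression.

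**The case against.** The best case on the other side is that RECIST 1.1 is already implied. Sections 6.3.4 and 6.3.5 define progressive disease, stable disease and duration of response in RECIST terms. Appendix B uses its own labels (irPD, irSD), while Section 8 speaks of progressive and stable disease without the prefix. Section 6.4 presents irRC as an addition. On this reading RECIST serves the endpoints and irRC governs only when treatment stops. It is the more natural reading, and it stands as an inference. It is not a rule: Section 6.3 applies both criteria to progression in general, and Section 8 never chooses.

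A reader might go further the other way and infer from Section 3.6.1 that irRC is the protocol's criterion for progression. That section decides removal from therapy; it does not define the endpoint, so it cannot settle the count.

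A reader might also infer that, because irPD needs confirmation, only progressions seen at week 9 could count by 5 months, so that almost any regimen would pass. The documents do not support this. It requires irPD to be dated at confirmation, which Appendix B does not say; it counts the interval from first documentation. It also requires that no week-18 progression is confirmed in time, that no death or clinical progression counts between week 9 and 5 months, and that the 5-month evaluation is a hard cut at 21.7 weeks.

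**Conclusion.** The point holds as an unresolved choice in the primary endpoint. The protocol applies two differing definitions of progression and names neither for the 3-of-10 and 6-of-17 counts. One discordant patient is enough to cross either boundary.

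The size is conditional. A rise in P(go) under the null from 0.094 to 0.185, 0.304 or 0.574 rests on three assumptions: the count is made under irRC, 5%, 10% or 20% of RECIST progressors remain progression-free under irRC, and the 20% null is a RECIST-type rate. Section 8 bases the null on previous trials with a 2.5-month median and does not say how progression was measured in them. It would be wrong to infer that the trial's actual error rate exceeds 10%: if one criterion is used and p0 and p1 refer to it, the design delivers 0.094 and 0.904 as planned.

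**What to change.** - In Section 8, state that the 5-month decision rule uses RECIST 1.1 progression (Section 6.3.4), dated at the first scan showing it, including for patients treated beyond it.
- State which criterion lay behind the historical 2.5-month median and confirm that it is comparable. If it is not, naming RECIST 1.1 does not by itself secure the 10% error.
- Report modified irRC progression, dated at first documentation, as a sensitivity analysis only.
- Reconcile the two confirmation intervals in Appendix B with each other and with the 9-week calendar.

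The treatment-removal rule need not change. Both readings are already planned, so no added patients and no change in sample size follow. The cost is a short amendment to Section 8 and Appendix B, and a reported rate that may be slightly less favourable than under irRC.

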6.3.1 Definitions

Evaluable for toxicity: All patients will be evaluable for toxicity from the time of their first treatment with pembrolizumab.

Evaluable for objective response: Only those patients who have measurable disease present at baseline, have received at least one cycle of therapy, and have had their disease re-evaluated will be considered evaluable for response. These patients will have their response classified according to the definitions stated below. (Note: Patients who exhibit objective disease progression prior to the end of cycle 1 will also be considered evaluable.)

Evaluable Non-Target Disease Response: Patients who have lesions present at baseline that are evaluable but do not meet the definitions of measurable disease, have received at least one cycle of therapy, and have had their disease re-evaluated will be considered evaluable for non-target disease. The response assessment is based on the presence, absence, or unequivocal progression of the lesions.

6.3.2 Disease Parameters

Measurable disease: Measurable lesions are defined as those that can be accurately measured in at least one dimension (longest diameter to be recorded) as ≥ 20 mm by chest x-ray, as ≥ 10 mm with CT scan, or ≥ 10 mm with calipers by clinical exam. All tumor measurements must be recorded in millimeters (or decimal fractions of centimeters).

Malignant lymph nodes: To be considered pathologically enlarged and measurable, a lymph node must be ≥ 15 mm in short axis when assessed by CT scan (CT scan slice thickness recommended to be no greater than 5 mm). At baseline and in follow-up, only the short axis will be measured and followed.

Non-measurable disease: All other lesions (or sites of disease), including small lesions (longest diameter <10 mm or pathological lymph nodes with ≥ 10 to <15 mm short axis), are considered non-measurable disease. Bone lesions, leptomeningeal disease, ascites, pleural/pericardial effusions, lymphangitis cutis/pulmonitis, inflammatory breast disease, and abdominal masses (not followed by CT or MRI), are considered as non-measurable.

Note: Cystic lesions that meet the criteria for radiographically defined simple cysts should not be considered as malignant lesions (neither measurable nor non-measurable) since they are, by definition, simple cysts.

‘Cystic lesions’ thought to represent cystic metastases can be considered as measurable lesions, if they meet the definition of measurability described above. However, if non-cystic lesions are present in the same patient, these are preferred for selection as target lesions.

Target lesions. All measurable lesions up to a maximum of 2 lesions per organ and 5 lesions in total, representative of all involved organs, should be identified as **target lesions** and recorded and measured at baseline. Target lesions should be selected on the basis of their size (lesions with the longest diameter), be representative of all involved organs, but in addition should be those that lend themselves to reproducible repeated measurements. It may be the case that, on occasion, the largest lesion does not lend itself to reproducible measurement in which circumstance the next largest lesion which can be measured reproducibly should be selected. A sum of the diameters (longest for non-nodal lesions, short axis for nodal lesions) for all target lesions will be calculated and reported as the baseline sum diameters. If lymph nodes are to be included in the sum, then only the short axis is added into the sum. The baseline sum diameters will be used as reference to further characterize any objective tumor regression in the measurable dimension of the disease.

Non-target lesions. All other lesions (or sites of disease) including any measurable lesions over and above the 5 target lesions should be identified as **non-target lesions** and should also be recorded at baseline. Measurements of these lesions are not required, but the presence, absence, or in rare cases unequivocal progression of each should be noted throughout follow-up.

6.3.3 Methods for Evaluation of Measurable Disease

All measurements should be taken and recorded in metric notation using a ruler or calipers. All baseline evaluations should be performed as closely as possible to the beginning of treatment and never more than 4 weeks before the beginning of the treatment.

The same method of assessment and the same technique should be used to characterize each identified and reported lesion at baseline and during follow-up. Imaging-based evaluation is preferred to evaluation by clinical examination unless the lesion(s) being followed cannot be imaged but are assessable by clinical exam.

Clinical lesions: Clinical lesions will only be considered measurable when they are superficial (e.g., skin nodules and palpable lymph nodes) and ≥ 10 mm diameter as assessed using calipers (e.g., skin nodules). In the case of skin lesions, documentation by color photography, including a ruler to estimate the size of the lesion, is recommended.

Chest x-ray: Lesions on chest x-ray are acceptable as measurable lesions when they are clearly defined and surrounded by aerated lung. However, CT is preferable.

Conventional CT and MRI: This guideline has defined measurability of lesions on CT scan based on the assumption that CT slice thickness is 5 mm or less. If CT scans have slice thickness greater than 5 mm, the minimum size for a measurable lesion should be twice the slice thickness. MRI is also acceptable in certain situations (e.g. for body scans).

Use of MRI remains a complex issue. MRI has excellent contrast, spatial, and temporal resolution; however, there are many image acquisition variables involved in MRI, which greatly impact image quality, lesion conspicuity, and measurement. Furthermore, the availability of MRI is variable globally. As with CT, if an MRI is performed, the technical specifications of the scanning sequences used should be optimized for the evaluation of the type and site of disease.

Furthermore, as with CT, the modality used at follow-up should be the same as was used at baseline and the lesions should be measured/assessed on the same pulse sequence. It is beyond the scope of the RECIST guidelines to prescribe specific MRI pulse sequence parameters for all scanners, body parts, and diseases. Ideally, the same type of scanner should be used and the image acquisition protocol should be followed as closely as possible to prior scans. Body scans should be performed with breath-hold scanning techniques, if possible.

PET-CT: At present, the low dose or attenuation correction CT portion of a combined PET-CT is not always of optimal diagnostic CT quality for use with RECIST measurements. However, if the site can document that the CT performed as part of a PET-CT is of identical diagnostic quality to a diagnostic CT (with IV and oral contrast), then the CT portion of the PET-CT can be used for RECIST measurements and can be used interchangeably with conventional CT in accurately measuring cancer lesions over time. Note, however, that the PET portion of the CT introduces additional data which may bias an investigator if it is not routinely or serially performed.

Ultrasound: Ultrasound is not useful in assessment of lesion size and should not be used as a method of measurement. Ultrasound examinations cannot be reproduced in their entirety for independent review at a later date and, because they are operator dependent, it cannot be guaranteed that the same technique and measurements will be taken from one assessment to the next. If new lesions are identified by ultrasound in the course of the study, confirmation by CT or MRI is advised. If there is concern about radiation exposure at CT, MRI may be used instead of CT in selected instances.

Endoscopy, Laparoscopy: The utilization of these techniques for objective tumor evaluation is not advised. However, such techniques may be useful to confirm complete pathological response when biopsies are obtained or to determine relapse in trials where recurrence following complete response (CR) or surgical resection is an endpoint.

Tumor markers: Tumor markers alone cannot be used to assess response. If markers are initially above the upper normal limit, they must normalize for a patient to be considered in complete clinical response. Specific guidelines for both CA-125 response (in recurrent ovarian cancer) and PSA response (in recurrent prostate cancer) have been published[83-85]. In addition, the Gynecologic Cancer Intergroup has developed CA-125 progression criteria which are to be integrated with objective tumor assessment for use in first-line trials in ovarian cancer[86].

Cytology, Histology: These techniques can be used to differentiate between partial responses (PR) and complete responses (CR) in rare cases (e.g., residual lesions in tumor types, such as germ cell tumors, where known residual benign tumors can remain).

The cytological confirmation of the neoplastic origin of any effusion that appears or worsens during treatment when the measurable tumor has met criteria for response or stable disease is mandatory to differentiate between response or stable disease (an effusion may be a side effect of the treatment) and progressive disease.

FDG-PET: While FDG-PET response assessments need additional study, it is sometimes reasonable to incorporate the use of FDG-PET scanning to complement CT scanning in assessment of progression (particularly possible 'new' disease). New lesions on the basis of FDG-PET imaging can be identified according to the following algorithm:

- a. Negative FDG-PET at baseline, with a positive FDG-PET at follow-up is a sign of PD based on a new lesion.
- b. No FDG-PET at baseline and a positive FDG-PET at follow-up: If the positive FDG-PET at follow-up corresponds to a new site of disease confirmed by CT, this is PD. If the positive FDG-PET at follow-up is not confirmed as a new site of disease on CT, additional follow-up CT scans are needed to determine if there is truly progression occurring at that site (if so, the date of PD will be the date of the initial abnormal FDG-PET scan). If the positive FDG-PET at follow-up corresponds to a pre-existing site of disease on CT that is not progressing on the basis of the anatomic images, this is not PD.
- c. FDG-PET may be used to upgrade a response to a CR in a manner similar to a biopsy in cases where a residual radiographic abnormality is thought to represent fibrosis or scarring. The use of FDG-PET in this circumstance should be prospectively described in the protocol and supported by disease-specific medical literature for the indication. However, it must be acknowledged that both approaches may lead to false positive CR due to limitations of FDG-PET and biopsy resolution/sensitivity.

Note: A ‘positive’ FDG-PET scan lesion means one which is FDG avid with an uptake greater than twice that of the surrounding tissue on the attenuation corrected image.

